## 2.5 [Symptom Frequency Analysis](#)

A univariate descriptive analysis was performed to quantify the frequency of individual symptoms and symptom families. This provided an overview of symptom burden and highlighted the most prevalent versus less common symptoms prior to exploring inter-symptom associations. Frequencies and proportions were summarized in tabular format, with descriptive comparisons by age, sex, and comorbidity status.

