Methodological advancements—including network analysis and factor-analytic techniques—have refined the detection of latent symptom structures in hemodialysis cohorts [6, 7, 9]. However, most studies rely on ordinal symptom scores. Only a minority employ tetrachoric correlations, which are well suited to dichotomous symptom data and may more accurately reflect latent interdependencies. Another major knowledge gap concerns the relationship between symptom patterns and comorbidities. Although comorbid conditions such as cardiovascular disease, diabetes, and pulmonary disorders are widespread in the hemodialysis population, their influence on symptom clustering remains inconsistent. Several large cohorts have reported only weak associations between comorbidity burden and symptom expression [15, 18], raising the possibility that symptom clustering reflects intrinsic patient-reported experiences rather than disease-driven phenotypes.

The need to address symptom burden in dialysis care has been reaffirmed by the KDIGO Controversies Conference on Symptom Management, which highlighted that fatigue, pain, pruritus, sleep disturbance, and emotional distress are common, disabling, and insufficiently

recognized in routine nephrology practice. KDIGO therefore recommended routine structured symptom assessment and emphasized that symptoms should be considered core clinical outcomes [21].

Increasing evidence also points to important sex-related disparities in symptom experience. Women undergoing hemodialysis consistently report higher levels of fatigue, psychological distress, and somatic symptoms. In our ePROMs study [22], female sex was independently associated with elevated stress (OR 2.27, 95% CI 1.00–5.14;  $p=0.05$ ) and prolonged post-dialysis fatigue recovery (OR 2.7, 95% CI 1.05–6.92;  $p=0.04$ ). These findings align with broader international data: according to the OECD's 2025 patient-reported indicator surveys, women consistently report lower physical and mental health scores, poorer well-being, and reduced social functioning—typically 6–15% lower—than men, with the smallest sex difference observed for self-management confidence [23]. Despite this, few nephrology studies have examined whether sex differences influence the structure of symptom clusters.

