In 2025, [name] et al. published the Concordance Study in *Clinical Kidney Journal*, a large multicenter cross-sectional study embedded within the French REIN registry. This study compared symptoms reported by hemodialysis patients using the Dialysis Symptom Index (DSI) with clinician-perceived symptoms, revealing a high symptom burden and marked patient–clinician discordance [3].

The present work is a secondary analysis of the Concordance Study dataset. Building on the original findings, this analysis aims to deepen understanding of symptom organization and determinants in hemodialysis using multivariate and correlation-based approaches. Specifically, our objectives were :

1. **to identify and characterize symptom clusters** using tetrachoric correlations and hierarchical clustering;
2. **to examine associations between symptoms (and clusters) and comorbidity burden**, while assessing potential **sex-specific patterns** in symptom expression.

Through this secondary analysis, we aim to clarify the internal architecture of symptom co-occurrence, identify key demographic drivers such as sex, and generate evidence supporting cluster-informed, individualized approaches to symptom assessment and management in routine nephrology care.

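### The protocol aims to identify sex as a demographic driver of symptoms, but the only analysis it describes by sex is a crude, one-factor-at-a-time descriptive table

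*Protocol*

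**What the plan says.** **Aims (Section 1).** The second numbered objective is to examine associations with comorbidity "while assessing potential sex-specific patterns in symptom expression". The closing paragraph adds the aim to "identify key demographic drivers such as sex", and the analysis is announced as a study of symptom organization and "determinants in hemodialysis using multivariate and correlation-based approaches".

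**Rationale (Section 1).** The protocol cites its own group's earlier study, in which "female sex was independently associated with elevated stress (OR 2.27, 95% CI 1.00–5.14"), and likewise "prolonged post-dialysis fatigue recovery (OR 2.7, 95% CI 1.05–6.92"). It then remarks that "few nephrology studies have examined whether sex differences influence the structure of symptom clusters".

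**Methods.** Section 2.2 lists sex among the extracted variables, with age, dialysis vintage and comorbidities. Section 2.5 opens with "A univariate descriptive analysis was performed to quantify the frequency of individual symptoms and symptom families" and ends with "Frequencies and proportions were summarized in tabular format, with descriptive comparisons by age, sex, and comorbidity status". Sex appears nowhere else in the Methods. Section 2.6 describes a tetrachoric matrix for symptoms and for families. Section 2.8 describes Ward clustering and Multiple Correspondence Analysis. Section 2.9 covers frequencies and the symptom-symptom and family-family correlations.

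**The concern.** The aims and the methods do not match in strength. To call sex a driver is to say that it matters in its own right. The rationale uses that standard too, since it cites independent associations from an earlier study. The planned comparison is crude and takes one factor at a time. If women and men in the sample differ in age, time on dialysis or comorbidity, a crude difference in symptom frequency mixes those differences with sex, and the table gives no means of telling them apart.

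At stake is one of the paper's main messages. A reader of the results could take a crude and possibly confounded difference as evidence that sex shapes symptom burden, and could set it beside the earlier study's independent associations as though the two were comparable.

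**Working it through.** **1. The plan's own figure.** Section 2.3: 256 records − 24 excluded = 232. This reproduces. The protocol gives neither the split by sex nor any symptom prevalence, so steps 4 to 6 rest on stated assumptions.

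**2. Where sex enters.**

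| Section | Content | Role of sex |
|---|---|---|
| 2.2 | Variables extracted | Recorded |
| 2.4 | Families and comorbidity groups | None; correlation testing is announced for comorbidity only |
| 2.5 | Univariate frequencies | Descriptive comparison |
| 2.6, 2.7 | Tetrachoric matrix and its reading | None stated |
| 2.8 | Ward clustering and correspondence analysis | None stated |
| 2.9 | Statistical analysis | None stated |

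The aim on sex therefore rests on Section 2.5 alone.

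**3. What that table estimates.** For a symptom Y and a covariate Z (say, age group), the crude difference is

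Σ P(Y | woman, z) P(z | woman) − Σ P(Y | man, z) P(z | man).

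This is a comparison at equal Z only if Z is distributed alike in both sexes or is unrelated to the symptom. Separate comparisons by age, by sex and by comorbidity do not show the joint distribution, so the reader cannot check either condition.

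**4. Is a sex estimate feasible at 232?** Assume 30 to 50% women, 20 to 50% prevalence in men, and the odds ratios quoted in Section 1 (2.27 and 2.7). Worked case with 40% women (93 women, 139 men) and 30% prevalence in men:

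- Odds in men 0.30/0.70 = 0.4286; × 2.27 = 0.9729; prevalence in women 0.9729/1.9729 = 0.493.
- Difference 0.193; standard error about 0.065 under both the null and the alternative.
- Power = Φ[(0.193 − 1.96 × 0.065)/0.065] ≈ 0.845.

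Over the whole assumed range, power is 0.734 to 0.859 at 2.27 and 0.885 to 0.959 at 2.7. These figures are unadjusted, two-sided at 5%, with no multiplicity correction.

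**5. Size of the models.** Sex, age and vintage make 3 terms (age and vintage taken as linear). The five comorbidity groups in Section 2.4 make 8. Six centres would add 5, giving 13. For a family with an assumed 20% prevalence there are 0.20 × 232 ≈ 46 events, that is 46/3 ≈ 15 per term in the first model, 46/8 ≈ 5.8 in the second and 46/13 ≈ 3.5 with centre. The first model is comfortable; the larger ones may be tight for rare, or nearly universal, families.

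**6. Precision of sex-specific correlations, should they be wanted.** At r = 0 and 50% prevalence, SE(r_t) = (π/2)/√n:

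- 70 women (30%): 0.188
- 93 women (40%): 0.163
- 116 women (50%): 0.146
- all 232 patients: 0.103

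With 139 men, SE = 0.133, so the difference between the sexes has SE √(0.163² + 0.133²) = 0.21, and a 95% interval of about ±0.41. Simulated at r = 0.4, the SE for 93 patients is 0.143 at 50% prevalence and 0.191 at 20%. The strong and weak bands in Section 2.7 lie only 0.2 apart (0.3 to 0.5), so one pair of symptoms can easily fall in different bands for men and women by chance.

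**The case against.** The best defence is that the second objective, read literally, asks about patterns in symptom *expression*. Section 2.5 tabulates individual symptoms and families by sex, which answers that at a descriptive level. This stands. A reader might infer that the sex part of the objective cannot be answered at all; the protocol does not support that. What the table cannot carry is the further aim about drivers.

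Three other strong readings also fail.

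- *That an adjusted model was promised and then omitted.* The word multivariate is met by clustering and correspondence analysis, and the independent associations belong to an earlier study.
- *That cluster structure by sex is an objective left without a method.* It appears only as a gap in the literature. The protocol does not commit itself to filling it.
- *That pooling men and women biases the matrix.* The protocol never says that they are pooled; that is inferred from the absence of any stratification. If they are, two symptoms that are independent within each sex would show a pooled r_t of only 0.06 to 0.08 at the quoted odds ratios, and 0.18 to 0.27 at their upper confidence limits (5.14 and 6.92), still below the 0.3 cut-off. Pooling could hide a real difference: hypothetical values of 0.6 in women and 0.2 in men pool to 0.33 to 0.41. Nothing in the protocol shows that such a difference exists.

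It may also be said that covariates and models belong in a statistical analysis plan, which is not shown. That is fair for the detail. But the protocol has its own statistical analysis section, describes its methods as already carried out on a fixed sample, and labels its one comparison by sex univariate and descriptive. The mismatch between aim and method is within this document.

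**Conclusion.** The point holds as a mismatch between a stated aim and the method given for it. The protocol can deliver crude sex differences in symptom frequency. It cannot, as written, identify sex as a driver, because no described analysis separates sex from age, dialysis vintage or comorbidity, and the data are cross-sectional.

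This rests on the text and not on a calculation. The size of any confounding cannot be given, because the protocol reports neither the sex split nor how the covariates differ by sex. The power and precision figures show only that an adjusted estimate is reasonable to attempt and that sex-specific correlations would be imprecise; both depend on the assumed share of women and prevalences. The point should be settled before the results are written up. It does not affect the main clustering analysis.

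**What to change.** 1. **Add an adjusted sex estimate.** Regress the total symptom count (Section 2.2) on sex, for example with a negative binomial model, and each of the eight symptom families (Section 2.4) with a logistic or robust-variance model. Adjust first for age and dialysis vintage. Add the comorbidity groups in a second model and report it separately, because comorbidity may lie on the path from sex to symptoms and the two models then answer different questions. Add centre if it is recorded: Section 2.1 mentions six centres, but Section 2.2 does not list centre among the extracted variables. Where a family has few events, keep to the smaller model or use a penalised fit. Report adjusted sex ratios with 95% confidence intervals beside the crude ones, labelled exploratory.
2. **Change the wording of the aim** in Section 1 from drivers to factors associated with symptoms.
3. **Settle the question of structure.** Either state that symptom structure by sex is not examined, or present sex-specific matrices as exploratory, with intervals for the coefficients.

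The cost is nine outcomes with two models each, using variables that Section 2.2 lists (centre apart), and a more modest stated aim. If the added models are not wanted, the least that would remove the mismatch is change 2 together with a sentence saying that the sex comparison is crude and descriptive.

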## 2.6 [Tetrachoric Correlation Analysis](#)

Associations between binary symptom variables were evaluated using tetrachoric correlation, which estimates the correlation between two dichotomous variables under the assumption of an underlying bivariate normal distribution. Tetrachoric coefficients ( $r_t$ ) range from  $-1$  to  $+1$ , with higher values indicating stronger positive co-occurrence. This method provides more accurate estimates of latent associations than Pearson or Spearman correlations for binary indicators.

A complete tetrachoric correlation matrix was generated for individual symptoms and symptom families. Pairwise correlations were inspected to identify symptom pairs with strong associations ( $r_t > 0.5$ ). Distance matrices ( $1 - r_t$ ) were subsequently constructed for use in clustering analyses.

## 2.7 [Interpretation of the Tetrachoric Correlation Matrix](#)

Correlation coefficients were interpreted as strong ( $r_t > 0.5$ ), moderate ( $0.3-0.5$ ), or weak ( $<0.3$ ). Strongly correlated symptoms tended to cluster together, suggesting shared physiological or experiential mechanisms (e.g., fatigue, sleep disturbance, appetite loss). Weak correlations indicated relatively independent symptom manifestations. Negative correlations—rare in this dataset—suggested mutual exclusivity or reversed binary coding. The tetrachoric matrix thus provided a robust foundation for exploring latent symptom structure in hemodialysis patients.

Overall, the tetrachoric correlation matrix provided a robust framework for identifying symptom clusters and characterizing the latent structure of symptom co-occurrence in the hemodialysis population.

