## 2.2 [Symptom Assessment](#)

Symptoms were assessed using the Dialysis Symptom Index (DSI), a validated self-administered instrument that captures 30 common physical and psychological symptoms in hemodialysis patients.

Each symptom was coded dichotomously (present = 1, absent = 0). A total symptom count was calculated for each participant. Sociodemographic and clinical characteristics—including age, sex, dialysis vintage, and comorbidities—were extracted from electronic medical records.

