## 2.3 [Data Preparation and Quality Control](#)

The initial dataset included 256 patient records. Data integrity was evaluated by screening for missing values and outliers. Twenty-four records with incomplete symptom data were excluded, yielding a final analytical sample of 232 patients. No additional inconsistencies were identified following internal validation and cross-checks.

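### Section 2.7 reads independence and mutual exclusivity into signed point estimates of r_t that carry no measure of uncertainty, and its bands give large negative values conflicting labels

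*Protocol*

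**What the plan says.** Section 2.6 of the protocol says that "Pairwise correlations were inspected to identify symptom pairs with strong associations", with 0.5 as the threshold. Section 2.7 sets three bands on r_t: strong above 0.5, moderate from 0.3 to 0.5, weak below 0.3. No absolute value is taken.

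Section 2.7 then gives the labels a meaning. Strong pairs point to shared mechanisms. For the weak band, "Weak correlations indicated relatively independent symptom manifestations". Negative coefficients, described as rare in these data, "suggested mutual exclusivity or reversed binary coding"; no minimum size is required for that reading. The section twice calls the matrix robust.

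Section 2.9 describes the scale and calls a value of -1 a strong negative correlation. None of these sections mentions a standard error, interval or resampling step for r_t.

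**The concern.** There are two problems.

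The first is in the wording and needs no data. Because the bands are signed, a coefficient of -0.8 lies below 0.3 and so counts as weak, hence relatively independent. Section 2.7 also reads it as mutual exclusivity or reversed coding, and section 2.9 treats the negative end of the scale as strong. These readings cannot all hold for one value.

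The second is precision. The labels carry statements about how symptoms relate, yet the sampling error of one tetrachoric coefficient at this sample size is about as wide as the bands. Failing to reach 0.3 is not evidence of independence, and falling below zero is not evidence that two symptoms exclude each other. At stake are the pair-level statements in the report: which symptoms go together, which stand alone and which exclude each other.

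**Working it through.** **Inputs from the protocol.** Section 2.3: "The initial dataset included 256 patient records" and "Twenty-four records with incomplete symptom data were excluded, yielding a final analytical sample of 232 patients"; 256 - 24 = 232, which reproduces. Section 2.2: the instrument "captures 30 common physical and psychological symptoms in hemodialysis patients". The eight families in section 2.4 add to 3 + 5 + 4 + 4 + 2 + 4 + 5 + 3 = 30, which agrees. Number of pairs: 30 × 29 / 2 = 435. The protocol states no precision target to reproduce.

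**Assumed.** Symptom prevalences are not given, so 10% to 50% is used as a range.

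**Standard error at true r = 0.** With thresholds estimated from the margins,

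SE = √(p₁q₁p₂q₂ / n) / [φ(z₁)φ(z₂)].

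- 50%/50%: (0.25 / √232) / 0.3989² = 0.01641 / 0.1592 = 0.103; half-width 1.96 × 0.103 = 0.20.
- 10%/10%: (0.09 / √232) / 0.1755² = 0.00591 / 0.0308 = 0.192; half-width 0.38.

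**Half-widths away from zero.** The delta method uses dr = (dp₁₁ - A dp₁ - B dp₂) / φ₂(h,k;r), with A = Φ((k - rh)/√(1 - r²)) and B = Φ((h - rk)/√(1 - r²)). The 95% half-widths at n = 232 are:

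| Prevalences | near r = 0.3 | near r = 0.5 |
|---|---|---|
| 50%/50% | 0.19 | 0.17 |
| 30%/30% | 0.21 | 0.18 |
| 20%/20% | 0.24 | 0.20 |
| 10%/10% | 0.32 | 0.27 |

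The whole moderate band is 0.5 - 0.3 = 0.20 wide.

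**Label probabilities.** These come from 4,000 simulated 2×2 tables per case, with 0.5 added to empty cells:

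| True r | Event | 50%/50% | 10%/10% |
|---|---|---|---|
| 0 | negative estimate | 50% | 51% |
| 0 | central 95% range | -0.20 to 0.20 | -0.36 to 0.34 |
| 0.2 | called moderate or strong | 15% | 27% |
| 0.4 | called weak | 13% | 27% |
| 0.4 | called strong | 13% | 24% |
| 0.6 | called moderate or weak | 10% | 23% |

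**Whole matrix.** True correlations were drawn from a normal distribution (mean 0.2 to 0.4, SD 0.15 or 0.20) and prevalences uniformly from 10–70% or 30–70%. Sampling error was added from the delta-method SE. Across these settings:

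- 19% to 32% of labels are wrong: 0.192 × 435 ≈ 84 to 0.321 × 435 ≈ 140 pairs. Errors of two bands stay below 1%.
- 72% to 89% of pairs have a 95% interval that crosses 0.3 or 0.5.
- 24% to 52% of pairs labelled weak have an interval that excludes zero.
- 45% to 82% of negative estimates come from a true value of zero or above.

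For a single case, an estimate of 0.29 at 50%/50% is labelled weak, yet its interval is about 0.29 ± 0.19, or 0.10 to 0.48. That is evidence against independence.

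**The case against.** Several stronger readings are tempting and do not hold.

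- **That every negative correlation is simply labelled weak.** The band taken alone does this, but section 2.7 gives negatives their own sentence. The defect is conflicting labels, and because the section calls negatives rare, few pairs are affected.
- **That the labels are mostly noise.** Setting every true correlation to 0.35 yields about 41 pairs called strong and 140 called weak, but that places every pair 0.05 from a cut-off. If every true value were 0.15, about 1 of 435 would be called strong and about 90% weak; at 0.65, about 95% would be called strong. A truly independent pair is called strong in about 0.1% of samples or fewer. The problem is blurring around the cut-offs.
- **That empty cells drive estimates towards -1.** At 5%/5% prevalence and true r = 0, the joint cell is empty in (1 - 0.0025)²³² ≈ 56% of samples. Whether that distorts r_t depends on the zero-cell correction, which the protocol does not state and a SAP may settle.
- **That sections 2.3 and 2.7 contradict each other.** Section 2.3 reports that "No additional inconsistencies were identified following internal validation and cross-checks". Listing reversed coding as a possible explanation is compatible with that, though it belongs in data checking.
- **That the bands shape the clusters.** Section 2.6 builds distances as 1 - r_t from the continuous coefficient, and section 2.8 is explicitly exploratory. The stated objectives concern clusters and their associations, not pair labels.

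It is also fair to say that intervals may appear in a SAP that is not shown, and that the wording is partly hedged. But the interpretation rule itself is fixed in section 2.7, and it works on point estimates. The correspondence analysis in section 2.8 checks clusters and does not protect pair labels.

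**Conclusion.** The point holds in a limited form. The signed bands give large negative coefficients incompatible labels; this follows from the text alone. Reading independence from a weak label, or mutual exclusivity from a negative sign, is not supported at n = 232, where one coefficient's 95% half-width near 0.3 (0.19 to 0.32) matches or exceeds the 0.20 width of the moderate band. About one in five to one in three labels could be off by one band. That share rests on assumed prevalences and assumed true correlations and cannot be fixed from the protocol. The consequence is confined to pair-level statements; the cluster solution is unaffected.

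**What to change.** In sections 2.6 and 2.7:

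1. Apply the bands to |r_t| and report the sign separately, which also brings section 2.7 into line with section 2.9.
2. Report a 95% interval for each r_t, for example from a bootstrap over patients, with the 2×2 counts for sparse pairs.
3. State that the bands describe the size of the estimate only.
4. Replace the independence statement for weak pairs with wording based on the interval.
5. Claim a negative association only where the interval excludes zero, and drop the mutual-exclusivity reading.
6. Resolve any suspected reversed coding as a data check before analysis, not as an interpretation of the result.

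A stricter rule, such as calling a pair weak only if its interval lies inside ±0.3, is not needed. At 10%/10% the half-width at zero is 0.38, so the rule could hardly ever be met; at 50%/50% it would need |r_t| of about 0.30 - 0.20 = 0.10 or less. Most weak pairs would be left without a label.

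The cost is a modest resampling step and some redrafting, with no new data. The report will make fewer firm statements about individual pairs.
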